4.3.3 Withdrawal from trial participation by sites

Should a site choose to close to recruitment the CI or PI must inform MAHSC-CTU in writing. Follow up as per protocol must continue for all patients recruited into the trial at that site and other responsibilities continue as per the written agreement between the trial sponsor and research site.

5.0 RECRUITMENT OF TRIAL PARTICIPANTS

5.1 Identifying Participants

Potentially eligible participants will be identified and approached whilst in hospital. A member of the patient's existing care team will first approach the patient about the trial and if they are interested then the Chief Investigator, Clinical Fellow or other appropriately trained staff (as assigned in the delegation log) will discuss the study with the patient. The participants must have been diagnosed with cerebrovascular disease and meet the inclusion criteria to be considered for this clinical trial.

Patients suffering ischaemic stroke will be eligible for screening. Initial screening will be for modified Rankin Scale 1-3 at time of screening. Patients otherwise satisfying inclusion / exclusion criteria will be recruited and an NIHSS and updated mRS assessment will be performed.

5.2 Consenting Participants

Patients deemed eligible for entry into the trial (after review of diagnosis, treatment history and key eligibility criteria) will be provided with a verbal and written explanation of the trial. The PI, or, where delegated by the PI, other appropriately trained site staff (GCP trained, suitably qualified and experienced), are required to provide a full explanation of the trial and all relevant treatment options to each patient prior to trial entry. During these discussions the information described in the Patient Information Sheet should be discussed with the patient. A contact number should be given to the patient, should they wish to discuss any aspect of the trial with site staff. This will be given to the patients on a patient card, that can be kept on their person at all times.

After adequate time has been given (a minimum of 24 hours), all queries have been addressed and the clinical team is confident that the patient understands the trial and all requirements, patients will be consented onto the trial signing a current approved written informed consent form. Written informed consent on the current approved version of the consent form for the trial must be obtained before any trial–specific procedures are conducted.

Four copies of the consent forms will be completed:

- 1. An **original, signed copy** of the patient consent form should be retained in the Investigator Site File.
- 2. A **copy** of the signed patient consent form should be retained in the patient notes.
- A copy of the signed patient consent form should be sent to the Wolfson Molecular Imaging Centre.
- 4. A **copy** of the patient consent form should be given to the patient.

The right of the patient to refuse to participate in the trial without giving reasons must be respected. All patients are free to withdraw at any time from the protocol procedures without giving reasons and without prejudicing further treatment. Patient withdrawal of consent from the trial must be explicitly documented in the source documents.

With the patient's permission, their GP will be informed of their patient's trial participation. If new safety information results in significant changes in the risk/benefit assessment, the patient information sheet and associated consent form would be reviewed and updated if necessary. If the patient information sheet and consent form is updated, at the discretion of the CI all patients (including those currently participating on the trial), would be informed of the new information, given a copy of the revised documents and if appropriate asked to re-consent to continue in the trial.

5.3 Screening for Eligibility

Pre-trial evaluations should be carried out as detailed below before registration. Clinical assessments should be performed within 4 weeks of initial CVD (cerebrovascular disease) diagnosis.

- 1. Diagnosis of CVD
- 2. Medical history, patients demographics and baseline symptoms
- 3. Concomitant medication (see details of prohibited medications in Appendix 1)
- 4. Vital signs: blood pressure, heart rate and rhythm, respiratory rate, temperature
- 5. Physical exam
- 6. MRI compatibility assessed by following standard practices as defined by local SOPs*

7. Pregnancy status assessed by following standard practices as defined by local SOPs*

* Not required for patients who fail the other screening points, so should be completed following successful completion of all other screening assessments.

5.4 Ineligible and non-recruited participants

Ineligible and non-recruited participants will be treated as per standard care at the discretion of the treating clinician. Best supportive care is recommended.

6.0 RANDOMISATION AND REGISTRATION PROCEDURES

Trial site(s) will be required to keep a record of all patients approached to participate in the study, in order to monitor recruitment. Details of patients approached and the number who declined participation should be provided to MAHSC CTU (summary details only, no identifiers will be collected). Details of patients who were consented to the trial but were found ineligible/ did not proceed for any other reason will also be collected by MAHSC CTU (in anonymised form using the screening log provided by MAHSC). Sites will be provided with instructions on how to provide this information to the CTU.

Any patient who consents to the trial and has been deemed eligible will be centrally randomised/registered by the MAHSC CTU. The clinical team at the research site will contact the CTU by a telephone call to a dedicated telephone number:

Randomisation/Registration line at MAHSC CTU: [name] (9am-5pm, Mon-Fri)

Sites should ensure that the following have been completed before randomisation/registration:

- Patient consent form must be signed
- Pre-registration evaluations must have been carried out at site as detailed in the previous section and the patient's eligibility for the trial must have been confirmed.

Randomisation and registration is completed within a bespoke computer system which is maintained by a MAHSC CTU statistician. A member of MAHSC CTU staff will access the system and check with the member of the clinical team calling that the patient's eligibility for the trial has been confirmed. The MAHSC CTU staff member will then provide the caller with verbal confirmation of the unique Participant ID assigned.

An e-mail confirmation of the participant entering into the trial will be sent to the designated circulation list by MAHSC CTU. The Participant ID will be used for the purpose of participant identification and data collection during the study.

Upon registration, participants will be given a trial specific participant card, which will have the trial title, participant ID number, contact details of the Principal Investigator and out of hours contact details in cases of emergency.

Phase 1 of the trial will require randomisation of the patients. Patients will be randomised 5:5 Arm A to Arm B. It is acknowledged that this randomisation process will not be completely random thus ensuring equal grouping. The caller will be given a unique ID for the patient as well as study ARM allocation, which will determine if the patient is having [¹¹C]-(R)-PK11195 on Day 1 or Day 2.

Phase 2 of the trial will only require registration of the patients. Therefore, the caller will be given a unique ID for the patient only.

7.0 RADIOTRACER & SCANNING DETAILS

7.1 Radiotracer summary

This study uses PET imaging with a new radiotracer ([¹⁸F]GE-180) that binds specifically to areas of inflammation. This will be used in combination with standard outcome assessments to see if there is a relationship between the degree and extent of inflammation with symptoms/functional impairment.

The new radiotracer [¹⁸F]GE-180, will be compared to an existing radiotracer known as [¹¹C]-(R)-PK11195. This also binds to sites of inflammation, and is widely used in other PET studies. [¹⁸F]GE-180 has a longer half-life and therefore has the potential to be used in routine clinics.

7.2 Radiotracer details

7.2.1 Details of trial treatment

- Name of radiotracers
 - [¹⁸F]GE-180 / [¹⁸F]GEH120714
 (S)-N,N-diethyl-9-(2-[18F]fluoroethyl)-5-methoxy-2,3,4,9-tetrahydro-1H-carbazole-4-carboxamide

o [¹¹C]-(R)-PK11195

(1-[2-chlorophenyl]-N-methyl-N-[1-methyl-propyl]-3-isoquinoline carboxamide)

• Description of the products

[¹⁸F]GE-180

Each vial contains ~10mL of an endotoxin and particle free solution of [¹⁸F]GE-180 in Formulation Buffer (GE Healthcare), with a radioactivity concentration of \leq 1100MBq / mL at end of synthesis. The maximum concentration of [¹⁸F]GE-180 will be 20µg per injectable volume. The total concentration of [¹⁸F]GE-180, known and unknown chemical impurities will not exceed 60µg per injectable volume.

[¹¹C]-(R)-PK11195

Each vial contains ~10mL of an endotoxin and particle free solution of $[^{11}C]$ -(R)-PK11195 in 0.9% saline. The concentration of $[^{11}C]$ -(R)-PK11195 will not exceed 10µg per injectable volume. The concentration of desmethyl $[^{11}C]$ -(R)-PK11195 (precursor) and total unknown impurities will each not exceed 3µg per injectable volume.

• Drug manufacturer

[¹⁸F]GE-180 and [¹¹C]-(R)-PK11195 are manufactured in accordance with EU Good Manufacturing Practice at the following facility:

Wolfson Molecular Imaging Centre (WMIC) The University of Manchester [name]

MIA(IMP) 35030 MS 35030

• How the drug will be supplied and packaged

The products are aseptically filtered into a type I glass vial sealed with a type I synthetic rubber closure and aluminium overseal. The product vial will be stored within a vial shield (lead or tungsten) in the absence of light at $\leq 25^{\circ}$ C.

The primary and secondary product packaging will be labelled by the manufacturer in accordance with Eudralex Volume 4, Annex 13 (Manufacture of Investigational Medicinal Products).

• Disposal of unused tracer material

Unused tracer material is monitored to determine the radioactivity content and the volume of material. A radioactive waste disposal document is completed that determines when the activity level will have decayed sufficiently for the material to be disposed of as non-radioactive chemical waste. The sample is held in a lead safe until it has decayed and is then double-checked with a radiation monitor prior to disposal. The procedure is outlined in the WMIC standard operating procedure: SOP_QC_00025 Disposal of Radioactive Samples Solid Chemical and Solvent Waste

7.3 Scanning summary

7.3.1 Magnetic Resonance Imaging (MRI)

In phase 1, MR imaging will be conducted using the Philips 1.5 Tesla Achieva MR Scanner at the Wolfson Molecular Imaging Centre (WMIC). It will consist of the following standard anatomical sequences (an approximately 30 min acquisition time slot required):

- T1 inversion recovery (IR) sequence
- T2 fluid-attenuated inversion recovery (FLAIR) sequence
- post-contrast enhanced T1 sequence

7.3.2 Positron Emission Tomography (PET) with [¹¹C]-(R)-PK11195

In phase 1, PET imaging will be conducted on the High Resolution Research Tomograph (HRRT) at the Wolfson Molecular Imaging Centre (WMIC).

Patient preparation: Patients may eat and drink normally on the day of the scan. As $[^{11}C]$ -(R)-PK11195 is a ligand for the peripheral benzodiazepine receptor, patients must not be taking Benzodiazepines with a long half-life that would interfere with the $[^{11}C]$ -(R)-PK11195 binding. A venous blood sample will be collected for the analysis of peripheral inflammatory markers.

A PET scanning session with [¹¹C]-(R)-PK11195 constitutes of:

- a short transmission scan of approximately 10 min to enable subsequent correction for photon attenuation in the head,
- followed by an emission scan with [11C]-(R)-PK11195 (approximately 60 min)

Tracer injection: A target dose of 740MBq (370MBq minimum) of [¹¹C]-(R)-PK11195 will be injected intravenously into the patient shortly after the emission scan starts;

Data acquisition: Dynamic PET data will be acquired over 60 min in list mode.

7.3.3 Positron Emission Tomography (PET) with [¹⁸F]GE-180

In phase 1 and phase 2, PET imaging will be conducted on the High Resolution Research Tomograph (HRRT) at the Wolfson Molecular Imaging Centre (WMIC). In phase 2 only 20 patients will have PET imaging with low dose head CT scan (1 minute) at Central Manchester University Hospitals NHS Foundation Trust instead of HRRT.

Patient preparation: Patients may eat and drink normally on the day of the scan. As [¹⁸F]GE-180 is a ligand for the peripheral benzodiazepine receptor, patients must not be taking benzodiazepines with a long half-life that would interfere with the [¹⁸F]GE-180 binding. A venous blood sample will be collected for the analysis of peripheral inflammatory markers and for the classification of the affinity of the binding to [¹⁸F]GE-180.

A PET scanning session with [¹⁸F]GE-180 constitutes of

- tracer injection outside the PET camera, a target dose of 200 MBq (120 MBq minimum) to be administered intravenously,
- followed by an uptake period of approximately half an hour during which a discrete venous blood sample may be taken for an assay of radioactivity
- participant to be placed in the camera for an emission scan of approximately half an hour (exact length still to be determined) acquired in list mode
- immediately followed by a short transmission scan of approximately 10 min to enable subsequent correction for photon attenuation in the head at the end of which another discrete venous blood sample may be taken for an assay of radioactivity

The total length of a PET scanning session with [¹⁸F]GE-180 is not to exceed two hours. The decision on the exact length of the tracer uptake waiting time and the emission scan is to be based on the experience provided by GE Healthcare from the evaluation of their first in man investigations with [¹⁸F]GE-180 and on the tolerability of the procedure by the study participants.

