1.1 Rationale for the proposed trial

There are two main objectives for the study; initially to evaluate whether a technique for microglial imaging is feasible and secondly to evaluate whether imaging of microglial activation predicts outcome and clinical progression in patients with stroke.

PET and the radiotracer [¹¹C]-(R)-PK11195 can provide a quantitative assessment of microglial activation in human subjects. [¹¹C]-(R)-PK11195 (1-[2-chlorophenyl]-N-methyl-N-[1-methyl-propyl]-3-isoquinoline carboxamide) is a specific ligand for the mitochondrial 18kDa translocator protein (TSPO), which is particularly abundant in activated microglia. Labelled with carbon-11 (¹¹C), the radiotracer has been used to image activated microglia in several neurological disorders including completed ischaemic stroke [Pappata *et al.* (2000), Garhard *et al.* (2005), Price *et al.* (2006), Thiel *et al.* (2010)]. Clinical and preclinical animal model data suggest that it is a very sensitive tool to monitor the evolution of microglial activation after a stroke demonstrating the early recruitment of microglia in the ischemic border zone and later involvement of the neocortex and thalamus [Myers *et al.* (1991)]. Unfortunately, the physical half-life time of ¹¹C (~20 min) is too short to allow routine clinical use of [¹¹C]-(R)-PK11195. This study however, will measure the extent of the inflammation in patients with stroke using positron emission tomography (PET) and a new radiotracer ([¹⁸F]GE-180) that binds specifically to activated microglia.

In the past few years, a new generation of tracer has been developed [Winkeler *et al.* (2010)]. (S)-N,N-diethyl-9-(2-[18F]fluoroethyl)-5-methoxy-2,3,4,9-tetrahydro-1H-carbazole-4-carboxamide (¹⁸F-GEH120714, [¹⁸F]GE-180) is a novel PET ligand with high affinity (0.87 nM) and selectivity for TSPO. Additionally, it has an *in vivo* performance superior to that of [¹¹C]-(R)-PK11195. Labelling with fluorine-18 (¹⁸F) that has a physical half-life of 110 minutes, makes it much more amenable for routine clinical use. [¹⁸F]GE-180 is being developed by GE Healthcare (patent WO2011117421) as a clinical PET biomarker of microglial activation.

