3.0 TRIAL DESIGN

3.1 Overall design

This study aims to recruit 50 patients in total receiving standard of care stroke assessments. Patients in phase 1 (n=10) will be asked to have two PET scans (using $[^{11}C]$ -(R)-PK11195 and

[figure not shown]
[¹⁸F]GE-180) and two MRI scans (one with and one without contrast). If the phase 1 analysis is favourable, the project will progress to phase 2. Patients in the second phase will be asked to have one PET scan (using [¹⁸F]GE-180) and two MRI scans (one with and one without contrast). All patients will remain on the study for 3 months after the onset of the stroke , at which point they will have outcome assessments (mRS and NIHSS). Following this, their participation in the study will cease and no further follow-up data will be captured. Patients will receive supportive care as per standard practice.

The study aims to recruit 10 patients in the first year, estimating a rate of 1 per month per NHS site, enabling 2 months for phase 1 review. Phase 2 estimated accrual for this study estimated at 2 patients per month. Thus, patient accrual is expected to be completed within 24 months. The total duration for phase 1 recruitment and analysis (12 months) analysis and phase 2 (24 months recruitment + 3 months for follow-up) recruitment is 39 months. The following 9 months will be dedicated to analysing the scans and completing coefficient correlation analysis on the outcome measure and the neuroinflammation. The total duration of the study is 48 months.

The study is designed to determine whether ¹⁸F-GE-180 PET as a biomarker can predict the clinical outcome in patients with cerebrovascular disease (CVD). Patients with sub-acute stroke of mild to moderate severity will be studied using standard research techniques and following the Quality Assessment of Diagnostic Accuracy Studies (QUADAS) criteria for diagnostic studies. In particular, the study protocol will ensure:

- patient selection based on standard diagnostic criteria
- short time interval between initial clinical assessment and PET
- verification of diagnosis at the time of follow-up
- independence of clinical diagnosis and clinical assessment from the result of the index test (PET) by blinding of clinical staff to PET results
- inclusion of failed and uninterpretable test results or withdrawal of consented patients into the final report

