11.3 Image analysis

The MR images will be used to assess the integrity of the blood-brain barrier and to provide anatomical information for a region-of-interest analysis of the PET images.

Dynamic PET data from the [¹¹C]-(R)-PK11195 scans will be processed as previously described (Su et al., 2013). Principally, characterisation of the radiotracer binding in the lesion target areas (infarct core and periphery, affected white matter tracts) will be based on the comparison with an appropriate reference region(s) in the contralateral hemisphere. Thus, each study participant serves as its own control avoiding the scanning of a separate control cohort in this clinical trial.

Summed PET images will be calculated from the [¹⁸F]GE-180 data, and for comparison by correlation analysis also of [¹¹C]-(R)-PK11195, enabling visual assessment and semi-quantitative analyses based on target-to-reference region ratios. Of particular interest is the quality of the [¹⁸F]GE-180 static images governed by the length of the image acquisition and the injected activity, two adaptable scanning parameters.

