All analyses of clinical outcomes in the stroke survivors will be carried out using the *regress* command of *Stata*, incorporating inverse probability weights to allow for attrition using Stata's *pweight* option. The statistical significance of any predictive effects will be evaluated using robust standard errors, p-values and associated confidence intervals (using the Huber-White 'sandwich' estimator). Prediction models include the relevant PET scan variable, TSPO Ala147Thr polymorphisms (high versus medium) and the possibility of an interaction between the two. Other baseline demographic and clinical covariates will be added to the model so that the 'unique' contribution of the PET scan data can be assessed (i.e. how much information does it provide over and above the routinely collected demographic and clinical variables?). We will be giving considerable attention to confidence interval estimation rather just relying on statistical significance.

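### GE-180 scans from two scanner systems (30 HRRT, 20 PET with CT) feed one PET predictor, and neither the stated model nor the image analysis accounts for scanner

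*Protocol*

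**What the plan says.** - **Patients.** Section 3.1: "This study aims to recruit 50 patients in total receiving standard of care stroke assessments". Ten are in phase 1 and 40 in phase 2. Section 2.0 says that data from the whole study will be used to relate inflammation to outcome.
- **Scanners.** Section 7.3.3 places GE-180 imaging in both phases on the HRRT, then makes an exception: "In phase 2 only 20 patients will have PET imaging with low dose head CT scan (1 minute"), done "at Central Manchester University Hospitals NHS Foundation Trust instead of HRRT". The session it describes includes a transmission scan of about 10 minutes for attenuation correction. The purpose of the CT is not stated.
- **Acquisition.** Section 7.3.3 gives "a target dose of 200 MBq (120 MBq minimum) to be administered intravenously" and leaves the uptake time and emission length open. Section 11.2 considers shortening the scan to 20 minutes. Section 11.3 calls acquisition length and injected activity "two adaptable scanning parameters". Emission data are acquired in list mode.
- **PET measure.** Section 11.3 uses target-to-reference region ratios from summed images.
- **Model.** Section 11.4: "Prediction models include the relevant PET scan variable, TSPO Ala147Thr polymorphisms (high versus medium"), with a possible interaction between the two. Further demographic and clinical baseline covariates are to be added but are not listed. Section 3.3 adds the baseline NIHSS.

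Nowhere does the protocol mention a scanner term, cross-calibration, resolution matching or an analysis by scanner.

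**The concern.** The protocol introduces a second imaging system for 40% of its patients and then writes down a model that takes no account of it. The lesion targets in Section 11.3 include the infarct periphery and white matter tracts. In such small regions a ratio can depend on spatial resolution, partial-volume loss and the post-injection window. A systematic difference between the two systems would then enter the predictor as variation unrelated to microglial activation.

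Section 11.1 names prediction of outcome from the baseline PET score as the main analytical question. It judges the design by how far the lower confidence limit for the correlation lies above zero. Extra variance in the predictor lowers both the correlation and that limit.

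Scanner is also partly confounded with phase, because every phase 1 patient is on the HRRT.

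This goes beyond detail that a statistical analysis plan would normally supply. Section 11.4 already fixes the software command, the weights, the standard errors and the named terms. Its open list is limited to demographic and clinical covariates, and scanner is neither.

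**Working it through.** **Inputs from the protocol.** N = 50 (Section 3.1); 20 patients on PET with CT (Section 7.3.3); rho = 0.40, n = 37, one-sided 90% limit of 0.200, and at least 40 analysable patients (Section 11.1).

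**Assumed input.** The offset d between scanners, in within-scanner SDs of the PET ratio. The documents give none, so a range of 0.25 to 1.0 is shown.

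**Step 1: the protocol's own figure.** The lower limit is tanh(atanh(r) − 1.2816/√(n − 3)).
- n = 37: tanh(0.4236 − 1.2816/√34) = 0.2011
- n = 36: 0.1979

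The stated n = 37 reproduces. At n = 40 the limit is 0.2098.

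**Step 2: the split.** 50 − 20 = 30 on HRRT (10 from phase 1 and 20 from phase 2), not counting replaced low binders. The PET-with-CT fraction is p = 20/50 = 0.4, so p(1 − p) = 0.24.

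**Step 3: effect of an ignored offset.** If the offset is unrelated to outcome, it adds 0.24·d² to a within-scanner variance of 1 and leaves the covariance with outcome unchanged. The pooled correlation is therefore 0.40/√(1 + 0.24·d²).

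| Assumed d (SD) | Pooled r | Lower limit at n = 40 | n for limit 0.20 |
|---|---|---|---|
| 0 | 0.400 | 0.210 | 37 |
| 0.25 | 0.397 | 0.206 | 38 |
| 0.5 | 0.389 | 0.197 | 42 |
| 0.75 | 0.375 | 0.182 | 48 |
| 1.0 | 0.359 | 0.164 | 58 |

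For example, d = 1 gives 0.40/√1.24 = 0.359, and the limit is tanh(0.3760 − 1.2816/√37) = 0.164.

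**Step 4: cost of a scanner term.** A partial correlation with k extra covariates uses √(n − 3 − k). With k = 1:
- n = 40: tanh(0.4236 − 1.2816/√36) = 0.207
- n needed for a limit of 0.20: 38

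With 10% deaths and 15% loss among survivors, the upper ends of the ranges in Section 11.4, 50 × 0.90 × 0.85 = 38.25 patients remain. At n = 38 with the scanner term the limit is 0.201, because √(38 − 3 − 1) = √34 as in Step 1.

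Like Section 11.1, these figures leave out the other covariates. Genotype, the interaction and baseline NIHSS use degrees of freedom with or without a scanner term.

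**Step 5: what separate analyses could show.** Scaling 40/50 to each group gives 24 and 16 patients. At r = 0.40 the limits are 0.143 and 0.068. Results by scanner can therefore support the adjusted model but cannot replace it.

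**The case against.** The strongest reply is that the offset is hypothetical and may be small. No figure in the documents supports 0.5 SD or more, and target-to-reference ratios cancel any pure scale difference. At 0.5 SD the limit is 0.197 against 0.200, which is a trivial shortfall. Scan length is under review in phase 1, list-mode data allow a common window to be chosen later, and reconstruction detail can sit in an imaging manual. The study also describes itself as primarily a feasibility study. All of this stands and limits the severity. It does not remove the gap: ratios leave resolution, partial volume and timing untouched, and the stated model has no place for scanner. Pooling is inferred from the single model and the use of whole-study data, and the role of the CT in attenuation correction is also an inference.

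A reader might infer more than the documents support:

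- **That time from stroke is wrongly omitted.** Section 1.1 calls the older tracer "a very sensitive tool to monitor the evolution of microglial activation after a stroke", and Section 5.3 says "Clinical assessments should be performed within 4 weeks of initial CVD" diagnosis. But that limit concerns clinical assessment, not PET. A stroke-to-PET window may be in the timeline figure that is not shown, and days from stroke could count as a clinical covariate.
- **That infarct volume must be in every model.** Section 11.4 measures the unique contribution of PET against routine demographic and clinical variables. Structural MRI would be a different benchmark. Section 1.0 also says that the inflammatory response contributes to the extent of tissue damage, so forced adjustment could remove part of the effect of interest.
- **That the two scanners create a false association.** A 1 SD offset combined with a 0.5 SD outcome difference between scanner groups would give an unadjusted correlation of about ±0.10 under a true zero. But no section says that patients are allocated to scanner by severity, and the planned baseline NIHSS adjustment would absorb much of such a difference.

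**Conclusion.** The point holds for scanner and harmonisation, at moderate severity. The protocol fixes two imaging systems in a 30/20 split, leaves acquisition settings adaptable, and states a model and an image analysis that take account of neither.

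The size depends on an offset that the documents do not give. Below about 0.4 SD the planned limit of 0.20 is still met at n = 40: the exact break-even is √(((0.40/0.3914)² − 1)/0.24) = 0.43 SD, where 0.3914 is the correlation whose limit is 0.20. At 1 SD the limit is 0.164, and 58 patients would be needed instead of 37. These figures assume a constant additive offset unrelated to outcome, and bivariate normality as in Section 11.1.

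The sample-size figure itself is correct. The documents do not support calling the main analysis invalid.

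**What to change.** - **Section 11.4:** include scanner (HRRT versus PET with CT) as a fixed term in every model containing the PET variable. Add a sensitivity analysis by scanner, for example separate estimates or a PET-by-scanner interaction, because a main-effect term removes a constant offset but not a different slope.
- **Section 11.3:** match HRRT images to the resolution of the PET-with-CT system. Compute ratios for all patients from one common post-injection window using the list-mode data, limited to the interval that all scans share. Record scanner, acquisition length and injected activity for each patient.
- **Optional:** a sensitivity model that adds MRI infarct volume. This is not a required correction.

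The cost is one degree of freedom (38 patients instead of 37 for a limit of 0.20; limit 0.207 instead of 0.210 at n = 40), some image reprocessing, and some loss of HRRT resolution in the matched images. No new data from patients are needed. The text should be settled before outcomes are linked to the scans.
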